#### Simultaneity Judgement (SJ)

Experimental setup includes two speakers placed 25 cm to the left and right of the participant's midline, and 30 cm from the body, integrated with two constant-current tactile stimulators (Digitimer DS7A) delivering non-painful vibrotactile stimuli via electrodes on each index finger. Auditory stimuli: 30 ms sound at 3,500 Hz. Tactile stimuli: single 100  $\mu$ s monophasic pulse.

Participants are blindfolded and seated comfortably. In each trial, auditory and tactile stimulus pairs are presented at random SOAs:  $\pm 5$ ,  $\pm 10$ ,  $\pm 15$ ,  $\pm 25$ ,  $\pm 40$ ,  $\pm 70$ ,  $\pm 120$ ,  $\pm 200$ ,  $\pm 350$  ms. Participants indicate whether stimuli were simultaneous by pressing designated keyboard keys. Four blocks of 144 trials each (576 total); associations between stimulus type, side, and response are counterbalanced.

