#### Simultaneity Judgement Training (SJT)

Differs from SJ in that participants receive feedback ("Correct!" or "Incorrect") after each response. SOA is initially set at 350 ms for ease and reduced after 3 correct responses or

increased after 1 error using a 40 ms staircase protocol. Each SOA is tested 30 times. Three blocks are administered with optional rest between them. Participants repeat SJ task before and after training.

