### **4. Statistical Analysis**

To confirm the study hypotheses, statistical analysis will be conducted in the following steps:

Pearson's correlation will be used to assess associations between formal characteristics of ritualized actions (J-Watcher scores), OCD symptom severity (Y-BOCS), childhood-adolescent trauma (CTQ), affectivity (HAM-D), pre-psychotic basic symptoms (FBF and SPI-A), personality traits (SCID-5-PD), temperament traits (TCI, ATQ), and functioning (SOFAS).

To evaluate the factors affecting overall functioning, in the case of significant correlations among the aforementioned variables, linear regression analyses (Enter Method) will be conducted, using SOFAS total score as the dependent variable and demographic variables and questionnaire scores as independent variables. The same analysis will be applied to assess variables involved in insight loss, using the total BABS score as the dependent variable.

Simultaneity Judgement will allow estimation of individual audio-tactile simultaneity ranges (SR). To obtain SR values, the percentage of simultaneous responses across all SOAs for each participant will be calculated. An Independent Channels Model will be fitted to each participant's response distribution. Unlike typical psychometric models (e.g., Gaussian, Logistic), ICM is generative and models underlying sensory and decisional processes.

This procedure will be conducted individually for each participant and stimulus combination. Data from individuals whose responses do not fit the ICM model significantly ( $p < 0.05$ ) will be excluded from further analysis. SR values from both experimental groups will then be compared and correlated with psychopathological scales using standard parametric (or non-parametric if data are non-normally distributed) tests.

For each participant, for each SOA, the median value will be calculated for the SR task pre- and post-training. This will determine how often participants correctly judged stimulus simultaneity and whether training improved accuracy. Median values from both groups will then be compared and related to psychopathological scale results.

Additionally, participants will undergo the Rubber Hand Illusion protocol with visuotactile stimulation. The resulting data will also be analyzed in relation to psychopathological variables using standard parametric (or non-parametric, if applicable) statistical tests.

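### The training analysis uses a per-participant, per-SOA median to show how often judgements were correct; on the natural reading that median can only be 0, 0.5 or 1, and a proportion should replace it

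*Protocol*

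**What the plan says.** The Simultaneity Judgement (SJ) section describes one outcome per trial: "Participants indicate whether stimuli were simultaneous by pressing designated keyboard keys". Each session has four blocks of 144 trials, 576 in all, spread over nine SOA magnitudes with both signs. The Simultaneity Judgement Training section adds: "Participants repeat SJ task before and after training".

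Section 4 (Statistical Analysis) treats these responses in two ways.

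- **Simultaneity range (SR).** "the percentage of simultaneous responses across all SOAs for each participant will be calculated", and an Independent Channels Model is fitted to each participant's response distribution. The resulting SR values are compared between groups and correlated with the scales.
- **Training effect.** "For each participant, for each SOA, the median value will be calculated for the SR task pre- and post-training". The stated purpose is: "This will determine how often participants correctly judged stimulus simultaneity and whether training improved accuracy". The next step is: "Median values from both groups will then be compared and related to psychopathological scale results".

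The protocol describes no other analysis of the pre/post change.

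**The concern.** How often a judgement is correct is a proportion. The median of a set of yes/no answers is not a proportion: it reports which answer was in the majority. A participant who is right on 70% of trials at an SOA and one who is right on 95% get the same median. Two participants just either side of 50% can get opposite ones. The statistic therefore does not measure what the section says it will show.

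Three results depend on it: the pre/post training change, the comparison of that result between groups, and its relation to the psychopathology scales.

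**Working it through.** **Inputs.** From the SJ section: 4 blocks of 144 trials; 9 SOA magnitudes with 2 signs; a binary response. The allocation of trials to SOAs is described only as random, so equal allocation is an assumption. The protocol gives no accuracy values, so every p below is an assumption used for illustration.

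**Step 1: trials per cell.** 4 × 144 = 576, which agrees with the protocol's total. SOA levels: 9 × 2 = 18. Trials per participant, SOA and session: 576/18 = 32. Per block: 144/18 = 8.

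**Step 2: median of 32 binary answers.** Let X ~ Binomial(32, p) be the number of correct answers. The median is 1 if X ≥ 17, 0.5 if X = 16, and 0 if X ≤ 15. The expected median is P(1) + 0.5 × P(0.5).

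| p | P(median = 0) | P(median = 0.5) | P(median = 1) | Expected median |
|---|---|---|---|---|
| 0.45 | 0.654 | 0.119 | 0.227 | 0.29 |
| 0.50 | 0.430 | 0.140 | 0.430 | 0.50 |
| 0.55 | 0.227 | 0.119 | 0.654 | 0.71 |
| 0.65 | 0.027 | 0.031 | 0.942 | 0.96 |
| 0.70 | 0.005 | 0.009 | 0.986 | 0.99 |
| 0.95 | 0.000 | 0.000 | 1.000 | 1.00 |

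The tie value 0.5 has probability at most 14.0% (at p = 0.50), so the median is 0 or 1 in at least 86% of cells at any p.

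**Step 3: what a training gain looks like.** The probability that the pre and post medians are equal is the sum over the three values of P(pre) × P(post), taking sessions as independent given p.

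- 65% to 95%: post is 1 with probability 1.000, so the probability of no change is 0.942 × 1.000 = 0.94. The proportion shows an expected change of 0.30, with SE = √[(0.65 × 0.35 + 0.95 × 0.05)/32] = √(0.275/32) = 0.093.
- 70% to 95%: no change with probability 0.986.
- 45% to 55%: no change with probability 0.654 × 0.227 + 0.119 × 0.119 + 0.227 × 0.654 = 0.31. The expected median moves from 0.29 to 0.71, against a true change of 0.10.

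**Step 4: the alternative reading, a median of the four block proportions (8 trials each), by simulation.**

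- The expected value moves from about 0.65 to 0.97 when p goes from 0.65 to 0.95, so a large gain is visible.
- Within one participant, the variance of the pooled proportion divided by that of the block median is 0.78-0.79 for p = 0.3 to 0.7 and 0.69 at p = 0.9. That is a loss of 21-31%.
- Group comparisons and correlations also carry between-participant variance s². The ratio becomes (V_prop + s²)/(V_med + s²). At p = 0.6, V_prop = 0.0866² = 0.0075 and V_med = 0.0977² = 0.0095. With s = 0.10 the ratio is 0.0175/0.0195 = 0.90; with s = 0.20 it is 0.0475/0.0495 = 0.96. Over p = 0.3 to 0.95 and s = 0.10 to 0.20, the loss is about 1-11%.

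**The case against.** The strongest objection is that section 4 never says what the median is taken over. It already reduces the same responses to percentages for the SR, and wording about how often judgements were correct suits a proportion. With four blocks per session there are several proportions per SOA of which a median could be taken. **This stands as a limit on certainty.** A reader might infer that the plan definitely takes a median of raw yes/no answers, or that training gains will necessarily be lost. The text does not establish either. The block reading is nowhere stated, though, and it is still less precise than the pooled proportion. A single percentage per SOA would leave nothing to take a median of, and no response time or graded rating is described for this task.

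A second objection is that the medians would not be constant even on the raw-answer reading. SOAs run from 5 to 350 ms in either direction, and the majority answer would typically switch somewhere along that range. **This stands:** the set of medians is coarse rather than uninformative. At any single SOA it still cannot show how often judgements were correct.

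A third objection concerns scope. A reader might infer that the group comparison and correlations for multisensory integration as a whole are compromised. They are not: SR values come from percentages and a fitted model, and are compared and correlated separately. The protocol's stated primary aims (sections 2 and 7) do not mention training. A reader might also infer 18 separate tests, one per SOA; section 4 does not state that.

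**Conclusion.** The point holds in a limited form. As naturally read, the training analysis fixes a statistic that cannot deliver its stated purpose: the median takes three possible values and shows only the majority answer. That limit does not depend on the assumed accuracies. The size of the distortion does: no change with probability about 0.94 for 65% to 95%, and an expected move from 0.29 to 0.71 for 45% to 55%. These figures also assume equal allocation of trials to SOAs.

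If a median of block proportions was intended, the harm is modest: 21-31% of within-participant precision, or about 1-11% after allowing for an assumed between-participant SD of 0.10-0.20. The proportion is the better choice on either reading. The effect is confined to the pre/post training change, its group comparison and its relation to the scales. This should be fixed, but it does not threaten the study's main results.

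**What to change.** In section 4, replace the median with the proportion of simultaneous (or correct) responses per participant, SOA and session. If correct responses are used, define the term: none of the 18 listed SOAs is 0 ms, so at every listed SOA the correct answer is that the stimuli were not simultaneous. Then analyse the pre/post change in these proportions, or in each participant's fitted SR, and use that change for the group comparison and the relation to the scales. A mixed-effects logistic model of the trial counts (session, group, SOA, session-by-group interaction, random participant effect) is one option, not a requirement.

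The cost is a few sentences. The trial-level responses are already to be collected, so no new data or procedures are needed.

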### **3. Materials and Methods**

#### *3.1 Recruitment*

This study will enroll subjects diagnosed with Obsessive-Compulsive Disorder (OCD) and Schizophrenia Spectrum Disorders who are attending the facilities of DAI-SMDP of AUSL Parma. Recruitment will take place from February 1, 2023 (following approval by the Ethics Committee) to February 1, 2026. Potentially eligible patients will be contacted (upon referral by their treating psychiatrists) and included in the study after confirming inclusion criteria and obtaining signed informed consent.

Sample size has been calculated based on previous studies aimed at investigating the formal and content aspects of OCD and the factors implicated in insight loss. Only upon stabilization of the psychopathological condition, all patients will be fully informed about the study's aims and procedures, and asked to sign the informed consent form.

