### 3.3e *Multisensory Integration*

All participants will complete the following tasks:

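### The before/after comparison of simultaneity judgements cannot show that training improved accuracy, because everyone is trained and no untrained or no-feedback repeat is described

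*Protocol*

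**What the plan says.** Section 3.3e applies its tasks to everyone: "All participants will complete the following tasks". The SJ task has "Four blocks of 144 trials each (576 total"), with no feedback mentioned. The training task is the same judgement with feedback and a staircase on the stimulus onset asynchrony (SOA): "Differs from SJ in that participants receive feedback ('Correct!' or 'Incorrect') after each response". On the order of tasks, the training section says: "Participants repeat SJ task before and after training".

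Section 4 then sets out the analysis: "For each participant, for each SOA, the median value will be calculated for the SR task pre- and post-training". It states the inference as "This will determine how often participants correctly judged stimulus simultaneity and whether training improved accuracy", and adds: "Median values from both groups will then be compared and related to psychopathological scale results". Section 4 does not define the two groups. Section 3.1 describes the enrolled population: "This study will enroll subjects diagnosed with Obsessive-Compulsive Disorder (OCD) and Schizophrenia Spectrum Disorders". The protocol calls the study observational and cross-sectional.

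**The concern.** Whether training improved accuracy is a causal question. Answering it needs some estimate of what a second SJ session would look like without training. The protocol describes no untrained group, sham training, no-feedback repeat or crossover.

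Before the retest, each participant has done a full SJ session and three training blocks. Performance may change through familiarity with the task, through tiredness, or because the participant has become more or less willing to answer that the stimuli were simultaneous. The plan credits the whole change to training.

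Two conclusions are at stake. A gain from practice alone could be reported as a training gain. A difference in change between the groups could be read as a difference in response to training when it reflects a difference in practice or fatigue.

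**Working it through.** **1. What the design identifies.** Section 4 states no figure for this comparison, so there is none to reproduce. For any participant,

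post − pre = training + practice + fatigue + criterion shift.

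One quantity is observed and there are several unknowns. Everyone follows the same order, so no contrast between participants removes a term. A larger sample estimates the sum more precisely but does not split it. For groups A and B, the difference in change is the difference in training effect plus the differences in the other three terms. It can show that change differs, but not why.

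**2. Trial counts.** Section 3.3e lists 9 SOA magnitudes with both signs: 9 × 2 = 18 SOAs. The stated 4 × 144 = 576 trials is consistent. If SOAs are equally allocated, which the text does not say (it says only that they are random), there are 144/18 = 8 trials per SOA per block and 576/18 = 32 per session.

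**3. Criterion shift.** The smallest listed SOA is ±5 ms; 0 ms is not listed. If a correct answer is defined by physical asynchrony (an assumption, since the protocol does not define it), answering not simultaneous is right on every SJ trial. A general move towards that answer would raise accuracy with no improvement in temporal perception. Feedback after each response could produce such a move.

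**4. Illustration of size.** Assume zero training effect and a practice shift of d standard deviations of the paired change. The chance that a two-sided 5% paired t-test is significant is P(|T| > t(0.975, n − 1)), where T is noncentral t with n − 1 degrees of freedom and noncentrality d√n. Both n and d are assumptions.

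| d | n = 30 | n = 40 | n = 60 |
|---|---|---|---|
| 0.2 | 0.19 | 0.24 | 0.33 |
| 0.3 | 0.36 | 0.46 | 0.63 |
| 0.5 | 0.75 | 0.87 | 0.97 |

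The nominal rate is 0.05. As a rough check at d = 0.3 and n = 30, the normal approximation gives Φ(0.3 × √30 − 1.96) = Φ(−0.317) = 0.376, close to 0.36.

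**5. Can the pre-training blocks supply the missing comparison?** One could fit a line to pre-training blocks 1 to 4, extend it to the post-training session, and call the excess the training effect. Assume a post-training session of four blocks and equal, independent block errors with variance 1.

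- *Precision.* The simple difference of two four-block means has variance 1/4 + 1/4 = 0.5. Blocks 1 to 4 have mean 2.5 and sum of squares 5. If the post-training blocks count as 5 to 8 (mean 6.5), the excess has variance 1/4 + 1/4 + (6.5 − 2.5)²/5 = 3.7, so its standard error is √(3.7/0.5) = 2.7 times as large. If the three training blocks also count as practice (post-training blocks 8 to 11, mean 9.5), the variance is 0.5 + (9.5 − 2.5)²/5 = 10.3 and the ratio is √(10.3/0.5) = 4.5.
- *Bias.* Let practice level off as 1 − exp(−x/τ), with x = 0 to 3 for the pre-training blocks and x = 4 to 7 for the post-training blocks, or 7 to 10 if training blocks count. Set the training effect to zero. Results are in units of the full practice range; the raw change is for x = 4 to 7.

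| τ (blocks) | Raw post − pre change | Excess over line | Excess, training blocks counted |
|---|---|---|---|
| 1 | +0.38 | −0.85 | −1.77 |
| 2 | +0.48 | −0.55 | −1.27 |
| 4 | +0.45 | −0.25 | −0.64 |

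The correct answer is 0 throughout. When practice levels off quickly, the extrapolation reports a false harm larger than the false gain it was meant to remove.

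**The case against.** **The claim is a small part of the study.** The objectives in Sections 2 and 7 concern ritual structure, insight, trauma and integration capacity, not training. This stands and limits the severity.

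**No practice effect is documented.** The SJ task mentions no feedback, which may keep practice gains small, and fatigue would usually lower post-training accuracy and so work against a false improvement. Section 4 also names no paired test. All this is fair. The table in step 4 is an illustration and does not predict what this study will find. But the documents do not show that practice is nil, and two biases in opposite directions cannot be assumed to cancel.

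**The text might allow a second baseline.** The instruction to repeat the SJ task before and after training could be read as an extra pre-training session. The length of the repeat is not given either. Section 4, however, uses only one pre-training and one post-training value, so that reading would not change the planned comparison.

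**An analysis plan could deal with it.** Modelling detail belongs there, but an analysis plan cannot create an untrained comparison, and step 5 shows that the obvious modelling substitute is imprecise and can be badly biased.

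**A stronger reading to avoid.** A reader might infer that the study will report a group difference as a difference in neural plasticity. Section 4 does not say so. Plasticity appears only as background in Section 1.3, and Section 4 says only that medians will be compared and related to the scales. It also leaves the two groups undefined, so calling them diagnostic groups is an inference.

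**Conclusion.** The point holds as a minor one. The sentence in Section 4 promises a conclusion about training that the design in Section 3.3e cannot support at any sample size. What the data can show is whether judgements changed after training, and whether that change differs between the groups.

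This rests on the document describing one fixed order, training for everyone, and no untrained or no-feedback repeat. It does not rest on the error rates in step 4, which depend on an assumed sample size and practice shift.

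The documents do not support the inference that training has no effect or that practice explains the change. They also do not support the inference that the four pre-training blocks already contain a usable correction: under the assumptions in step 5, the standard error grows 2.7 to 4.5 times, and the estimate is biased if practice levels off.

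**What to change.** In Section 4, replace the claim about training with wording such as: *change in simultaneity judgements after training (training, practice and criterion shift combined)*. Limit the group comparison to whether that change differs between the groups, without attributing a difference to training. Do not use a linear trend extrapolated from pre-training blocks 1 to 4 as the training estimate.

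The cost is one or two sentences, with no new data or analysis. What is given up is a causal statement that the design could not support. If the sponsor wants that statement, it needs a design change, namely an SJ repeat without training or without feedback (a comparison group or a planned second baseline). That adds testing time or participants, and the stated objectives do not require it.

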## **5. Data Collection and Confidentiality**

Both the Clinical Records Form (CRF) and questionnaire/task results will be collected electronically. All costs will be covered by the UOC University-Affiliated Psychiatric Services. Only the study investigators will have access to the data. Interviews and questionnaires will be conducted in a designated room on the first floor of [name], Ospedale Maggiore di Parma.

Identifying information (name and date of birth) will be used only for patient scheduling and consent. Upon enrollment, patients will receive a unique ID code used to anonymize all data. A separate file containing ID-name correspondence will be stored by the Principal Investigator on a password-protected computer in a locked office.

[name] will be responsible for data archiving, protection, and final reporting. All investigators will participate in data analysis and preparation of scientific publications.

## **6. Safety Concerns**

No anticipated risks, physical or psychological consequences are expected from this study, which will not interfere with standard clinical care. Patients will continue to be monitored and treated by their usual clinical providers.

During questionnaire completion, some participants may temporarily experience sadness, discouragement, or irritation when recalling unpleasant past experiences. However, any such emotions are unlikely to last beyond the duration of the session. Patients may discuss their concerns at any time with a study physician.

Thus, study-related risks are not greater than those encountered in daily life. Participation is voluntary and can be withdrawn at any time. Any damages (attributable to AUSL Parma or its

personnel during the study) are covered under the Regional Risk Management Program for public health entities.

## **7. Conclusions**

The primary aim of this study is to comprehensively assess the formal and content-related features of OCD symptomatology and its relation to Schizophrenia Spectrum Disorders, in order to identify patient subgroups that may respond more effectively to treatment.

Special focus will be given to the structure of compulsive rituals and poor-insight OCD forms, evaluating their clinical characteristics and severity, and exploring potential predisposing factors.

These factors include personality and affective traits, as well as the possible etiopathogenetic role of stressful or traumatic experiences during childhood-adolescence in predisposing individuals to OCS or OCD spectrum disorders based on neurobiological vulnerability or influencing their clinical presentation.

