### **Study Design:**

Observational (medication-free), cross-sectional, multicenter

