#### *1.1c The Role of Trauma*

Childhood trauma is considered a common risk factor for several psychiatric disorders: Mood Disorders, Substance Use Disorders, Psychotic Disorders Eating Disorders, and Personality Disorders.

Studies have also indicated a link between various types of childhood trauma—especially emotional abuse and emotional neglect—and the development of OCS. A causal relationship between traumatic events and the onset of symptoms has also been hypothesized.

However, the mechanism by which childhood-adolescent trauma may predispose individuals to OCS development remains underexplored. A recent study by Bey et al. (2017) proposed a possible link between childhood trauma and specific temperamental traits: particularly, high levels of "harm avoidance" are considered a premorbid vulnerability factor and an endophenotype of OCD.

The objective of this study is to retrospectively explore the possible presence of childhood and adolescent trauma in OCD patients using dedicated scales and to assess whether such trauma may have a predisposing role in the onset of OCS or OCD spectrum disorders, or a pathoplastic role in shaping clinical manifestations.

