## **2. Rationale and Study Hypotheses**

The primary objective of this study is to conduct a comprehensive investigation of the psychopathology of the Obsessive-Compulsive Spectrum, exploring not only the content characteristics of obsessive-compulsive symptoms, but also the formal modalities of expression—particularly the structure of the compulsive ritual—and how these aspects may affect the individual's global functioning.

Additionally, the study aims to assess possible predisposing factors to loss of insight in OCD, particularly the potential etiopathogenetic role of trauma, personality traits, affective factors, or OCD severity, with the goal of identifying subgroups of patients who may be more responsive to therapy.

Furthermore, it seeks to evaluate how patients with OCS and schizophrenia-spectrum symptoms respond to multisensory stimuli (auditory, tactile, and audio-tactile), in order to identify correlations between their capacity for audiovisual-tactile integration and psychopathological variables—especially trauma—and the structure of the ritual. A deficit in the ability to integrate signals at the cortical level could lead to unreliable perceptions, which may be a core feature of the illness, from which obsessive phenomena such as the need for checking and repetition emerge.

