##### *3.3a Clinical and Demographic Variables*

Participants will complete a questionnaire including age, sex, years of education, family status, employment status, and housing situation. Through an initial brief interview and data retrieved from clinical records, information will be extracted on diagnosis at onset, initial treatment, family history, age at onset, and current therapy. A clinician-rated scale evaluating patient functioning (SOFAS) will also be completed. Lastly, the number of monthly visits to the relevant service will be recorded.

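### Two stated goals, treatment-responsive subgroups and a predisposing role of childhood trauma in onset, are not supported by the cross-sectional, patients-only design

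*Protocol*

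**What the plan says.** The Protocol describes its design as "Observational (medication-free), cross-sectional, multicenter".

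**Treatment response.** Section 7 gives the primary aim a purpose: "in order to identify patient subgroups that may respond more effectively to treatment". Section 2 attaches the same purpose to the study of insight loss: "with the goal of identifying subgroups of patients who may be more responsive to therapy".

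**Trauma.** Section 1.1c sets the objective "to assess whether such trauma may have a predisposing role in the onset of OCS or OCD spectrum disorders" and continues with an alternative, "or a pathoplastic role in shaping clinical manifestations". Section 7 repeats both halves. Section 2 adds a third question: "the study aims to assess possible predisposing factors to loss of insight in OCD, particularly the potential etiopathogenetic role of trauma".

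**Data.** Section 3.3a takes from interview and records "diagnosis at onset, initial treatment, family history, age at onset, and current therapy". Section 3.2a admits adults with OCD, a schizophrenia spectrum disorder, or both. Section 3.3b describes the CTQ as retrospective. Section 4 plans Pearson correlations among the scales and regressions with functioning (SOFAS) and insight (BABS) as dependent variables.

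**The concern.** A stated goal needs a variable that measures its outcome and a contrast that bears on it. The response goal appears to lack the variable, and the trauma-onset goal appears to lack the contrast. If so, a report that follows the protocol could present subgroups as likely responders, or trauma as a cause of onset, with nothing in the data to support either statement. A larger sample would not help. Nor could a statistical analysis plan supply a response measure that the protocol does not collect.

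**Working it through.** No arithmetic applies beyond a count, and the protocol gives no figure on this point to reproduce. The check sets each goal beside the population, the measurements and the analyses.

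**1. Subgroups that respond better to treatment**

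- *Treatment data (3.3a):* initial treatment and current therapy. These record what was given, not what followed.
- *Instruments (3.3b and 3.3c):* 5 self-administered questionnaires plus 6 clinician-administered instruments make 11. None is described as measuring response or remission, and none is scheduled twice. The Y-BOCS is described as a severity scale, with no earlier baseline.
- *Repeated measurement (3.3e):* the only before-and-after measurement is the simultaneity judgement task around perceptual training. It measures learning on that task, not response to treatment.
- *Care (section 6):* patients stay with their usual providers, and treatment is not studied.
- *Analysis (section 4):* the dependent variables of the regressions are SOFAS and BABS.

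Result: no response variable and no response analysis.

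**2. Trauma as a predisposing factor for onset of OCS or OCD**

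- *Population (3.2a):* everyone has at least one of the two disorders, and no unaffected group is described.
- *Exposure (3.3b):* the CTQ is completed by people who are already ill, about their childhood and adolescence.
- *Analysis (section 4):* the CTQ is correlated with ritual structure, symptom severity, depression, basic symptoms, personality, temperament and functioning, and it may enter the SOFAS and BABS regressions. The explicit group comparisons concern the simultaneity tasks. None is stated for the CTQ.
- *Possible internal comparison:* patients with a schizophrenia spectrum disorder but no OCD could serve as a reference group, but section 1.1c itself counts psychotic disorders among those for which childhood trauma is a risk factor. If trauma raises the risk of both conditions, comparing one with the other need not show how trauma relates to OCD against an unaffected population.

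Result: no contrast on onset is planned, and the one available internally is not a clean one.

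**3. Trauma in relation to clinical presentation and insight**

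CTQ, Y-BOCS, BABS and J-Watcher scores all vary among patients, and section 4 provides correlations and a BABS regression. An association can be estimated; its temporal order or causal direction cannot.

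Result: answerable as a cross-sectional association.

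**The case against.** **The response wording is a purpose, not an endpoint.** Both clauses say only that patients may respond. In section 2 the sentence that names the primary objective does not mention response, and section 4 promises no response analysis. Profiling patients by insight could be a first step, since section 1.1b cites literature on insight and treatment response. This stands to the extent that no planned result is biased. It does not rescue the goal. Section 7 ties it to the primary aim, and section 1.1b reports that the literature conflicts: some authors found poorer response with poor insight, others no difference. Finding a poor-insight subgroup is therefore not finding a less responsive one.

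**The trauma objective is wider than onset.** This stands. The question of clinical presentation and that of insight loss can be studied among patients. Section 1.1c also proposes temperament as the link between trauma and OCD, and the planned CTQ and TCI correlations bear on that as an association.

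**Readings that go too far.**

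- A reader might infer that everyone enrolled has OCD, so that no comparison by OCD status is possible. Section 3.2a does not support this: some participants may have a schizophrenia spectrum disorder alone.
- A reader might infer that the CTQ is related only to current symptom severity. Section 4 also relates it to personality, temperament, functioning and ritual structure.
- A reader might infer that age at onset is never used. It is collected under the clinical and demographic variables, and section 4 does not list which of these enter the regressions. It is not named as an outcome, but more than that cannot be said without the analysis plan.

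**Conclusion.** The point holds for two goals. The data planned carry no information on treatment response, because no listed variable measures it. On trauma and the onset of OCS or OCD, the planned analyses give associations among people who are already ill, with recalled exposure and no unaffected reference group, and these cannot show predisposition.

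It would be wrong to conclude that every trauma aim fails, or that the planned correlations and regressions are invalid. The aims on clinical presentation, insight and functioning survive as cross-sectional associations.

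This should be corrected because it changes what the study may conclude, although it leaves the planned analyses as they are. The verdict assumes that the protocol's lists of measurements and groups are complete. It depends on no sample size or effect size.

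**What to change.** 1. In sections 2 and 7, delete the treatment-response goal or label it a hypothesis for later longitudinal work. Keeping it as an aim of this study would need a response measure, which the protocol does not describe.
2. In sections 1.1c, 2 and 7, replace the predisposing or etiopathogenetic role of trauma with association.
3. Optionally add two analyses, labelled exploratory and drawn from data already collected:
   - a comparison of CTQ scores by presence of OCD or OCS, for example within schizophrenia-spectrum patients, adjusted for age and sex;
   - the association of CTQ with age at onset.
4. State the limits of both. The first compares people who are all ill with a condition for which trauma is itself a risk factor. The second uses cases only, so it has no contrast on onset, and reported trauma may have followed an early onset. Neither establishes onset or causation. The protocol gives no group sizes, so whether the first comparison is feasible must be checked against actual enrolment.

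The cost is a few changes of wording, a more modest claim and, if step 3 is taken up, a little extra analysis. No new assessment of patients is needed.
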